#### 4. SUMMARY OF STUDY DESIGN

In this Phase 3 clinical study, approximately 1,083 subjects with mild-to-moderate AD (361 per arm) will receive placebo or 50 mg tablets of simufilam or 100 mg tablets of simufilam, twice daily, for 76 weeks. Randomization (1:1:1) will be stratified by low or high MMSE (16-20 and 21-27).

Subjects, 50-87 years of age, will be selected for screening based on a diagnosis of AD consistent with Stages 4 or 5 on the Alzheimer's continuum (National Institute on Aging – Alzheimer's Association 2018). Subjects must have MMSE  $\geq$  16 and  $\leq$  27, and a Clinical Dementia Rating Global Score (CDR-GS) of 0.5, 1 or 2. Finally, subjects must have confirmed PET or fluid biomarker evidence of AD pathophysiology prior to randomization (see Section 5.2 – Inclusion Criteria for details).

Once subjects have been satisfactorily screened for study participation, visits to the research clinic will occur on Study Day 1 and at Weeks 4, 16, 28, 40, 52, 64 and 76.

The co-primary endpoints include the 12-item Alzheimer's Disease Assessment Scale – Cognitive Subscale (ADAS-Cog12) and the Alzheimer's Disease Cooperative Study – Activities of Daily Living (ADCS-ADL), both assessed as the change from baseline to the end of the double-blind treatment period (Week 76).

Secondary endpoints include the integrated Alzheimer's Disease Rating Scale (iADRS), Neuropsychiatric Inventory (NPI), MMSE, and Clinical Dementia Rating Sum of Boxes (CDR-SB). A brief questionnaire assessing caregiver burden, the Zarit Burden Interview (ZBI), will be collected as an additional secondary endpoint.

Safety will be evaluated by adverse event monitoring, vital signs, clinical labs, and the Columbia Suicide Severity Rating Scale (C-SSRS) at every visit. Subjects will undergo MRI during screening to ensure entry criteria are met (unless recent MRI confirms entry criteria); however, 150 subjects (50 subjects per treatment group) will also undergo repeat MRI assessments at Weeks 40 and 76 to assess both long-term safety and drug impact on brain volume as noted above. Resting ECGs will be conducted at Baseline (Study Day 1) and Weeks 4, 40 and 76. A complete physical and neurological examination will be performed at screening, and brief examinations will be performed at all other visits. Weight will be measured during the Screening Period, at Baseline (Study Day 1) and at all other visits.

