6.1.5. Analysis Visit Windows

All scheduled visits and associated variables for the treatment phase will be analyzed based on the study week to which they are assigned.

For the safety summaries and analyses, scheduled analysis visits will be windowed to the nearest scheduled visit and the unscheduled visits/assessments and early termination visits will be mapped to a scheduled visit using the following visit windows (Table 2.1 and Table 2.2). Visit windows will be assigned by splitting the periods between visits at the mid-point between the visits.

If both scheduled and unscheduled visits fall within the same visit window, scheduled visit will be used over unscheduled visits. If both scheduled and early termination visits fall within the same visit window, the data from the early termination visit will supersede.

If more than one unscheduled visit falls within the same visit window, the one closest to the target date will be used in the analysis. If equidistant, the earliest visit will be used.

If the analysis visit (for Unscheduled or ET assessments) falls on a visit window in which that specific assessment is not scheduled, then that assessment will not be used for analysis.

Table 2.1: Visit Windows for Safety (Except for ECG) Analysis

Scheduled Visit	Scheduled Visit Day	Window for Assignment of
	(Target Day)	Analysis Visit (Study Days ¹)
Week 4	Day 29	Day 2 – Day 71
Week 16	Day 113	Day 72 – Day 155
Week 28	Day 197	Day 156 – Day 239
Week 40	Day 281	Day 240 – Day 323
Week 52	Day 365	Day 324 – Day 407
Week 64	Day 449	Day 408 – Day 491
Week 76	Day 533	Day 492 – Day 575

¹Study Day relative to the date of first dose of study drug.

Table 2.2: Visit Windows for Safety (ECG only) Analysis

Scheduled Visit	Scheduled Visit Day	Window for Assignment of
	(Target Day)	Analysis Visit (Study Days ¹)
Week 4	Day 29	Day 2 – Day 155
Week 40	Day 281	Day 156 – Day 407
Week 76	Day 533	Day 408 – Day 659

¹Study Day relative to the date of first dose of study drug.

For the efficacy summaries and analyses, scheduled analysis visits are visits upon scheduled time points as specified in the Schedule of Time and Events. Scheduled analysis visits will be windowed

Version 1.0 | 28-Feb-2025 Page 21 of 56

to the nearest scheduled visit. Assessments that fall within the same window will be averaged. There will be one valid value of assessment kept for each scheduled analysis visit in summary / analysis statistics.

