9.6. Concomitant Medications

Concomitant medications will be summarized descriptively by treatment group using the number and percentage of participants by Anatomical Therapeutic Chemical class (ATC level 2) and preferred term (ATC level 4).

All "Cognitive enhancers" defined by verbatim terms: donepezil (Aricept, Adlarity), galantamine (Razadyne, Reminyl), rivastigmine (Exelon) and memantine (Namenda, Ebixa, Nemdatine) will be summarized separately. All concomitant medication data will be listed. The cognitive enhancers

Version 1.0 | 28-Feb-2025 Page 37 of 56

will be flagged in the concomitant medication listing.

9.7. **MRI**

Descriptive summaries of MRI findings will be presented by treatment group with number and percentage of participants for presence of CS MRI abnormalities, total number of MH, total number of new MH, and total number of resolved MH at the following visits. The Persistence and new occurrence of MRI abnormality will be presented by treatment group at week 40 and week 76.

Baseline, Week 40 and Week 76/ET/ED.

The descriptive analysis will be presented for those subjects who signed consent for MRI substudy.

The MRI findings will be listed.

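### MRI safety findings have no visit windows of their own, so early-termination or unscheduled scans outside Days 240-323 and 492-575 are left out of the MRI safety summary

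*SAP*

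**What the plan says.** Protocol Section 4 has 150 participants (50 per group) repeat MRI at Weeks 40 and 76 "to assess both long-term safety and drug impact on brain volume". Appendix A shows no other post-baseline MRI, and its last column combines Week 76 with ET/ED.

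SAP 6.1.5 has two safety window tables: "Table 2.1: Visit Windows for Safety (Except for ECG) Analysis" and "Table 2.2: Visit Windows for Safety (ECG only) Analysis". MRI findings are reported in the safety chapter (SAP 9.7) and in safety Table 14.3.11.1, so the first table governs them. The section's exclusion rule names unscheduled and ET assessments: one that "falls on a visit window in which that specific assessment is not scheduled, then that assessment will not be used for analysis".

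SAP 4.2 sends ET data through these windows and creates no separate ET category. SAP 9.7 gives the MRI visits as "Baseline, Week 40 and Week 76/ET/ED", while its sentence on persistence and new occurrence mentions only Weeks 40 and 76. SAP Section 5 admits to the MRI set anyone who signed the sub-study consent and has a single usable scan after baseline.

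**The concern.** In safety summaries the exclusion bears almost only on MRI. Laboratory tests, vital signs, weight, brief examinations and C-SSRS are done at every visit, so Table 2.1 always has a place for them. ECG has a sparse schedule, and Table 2.2 covers it without a gap. MRI is the other sparse post-baseline safety assessment, and it has no table. This looks like an oversight.

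What is at stake is the count of new microhemorrhages and new clinically significant abnormalities. The scans left out come from participants who stopped early or were scanned off schedule, and an off-schedule scan may have been prompted by a clinical event. The rule also separates the analysis set from its own table: a participant whose only post-baseline scan is an ET scan on Day 365 is in the MRI set but contributes no post-baseline result.

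**Working it through.** Inputs: the target days in SAP Table 2.1 (29, 113, 197, 281, 365, 449, 533); the rule "Visit windows will be assigned by splitting the periods between visits at the mid-point between the visits"; and the post-baseline MRI schedule, Weeks 40 and 76.

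Step 1, reproduce the windows. Each upper bound is the mid-point of adjacent targets, e.g. (29 + 113)/2 = 71 and (281 + 365)/2 = 323. The last window runs half an interval past its target: 533 + 84/2 = 575. Every bound of Table 2.1 is returned. The same rule on the ECG targets (29, 281, 533) gives 155, 407 and 533 + 126 = 659, as in Table 2.2.

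Step 2, mark where MRI is scheduled.

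| Window | Days | Length | MRI scheduled |
|---|---|---|---|
| Week 4 | 2-71 | 70 | no |
| Week 16 | 72-155 | 84 | no |
| Week 28 | 156-239 | 84 | no |
| Week 40 | 240-323 | 84 | yes |
| Week 52 | 324-407 | 84 | no |
| Week 64 | 408-491 | 84 | no |
| Week 76 | 492-575 | 84 | yes |

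Step 3, count. Total 70 + 6 × 84 = 574 days. Usable: "Day 240 – Day 323" and "Day 492 – Day 575", 2 × 84 = 168. Excluded: 574 − 168 = 406, and 406/574 = 70.7%. Up to the end of the Week 76 visit allowance (Day 533 + 5 = 538) it is 406/537 = 75.6%. ECG, and assessments done at every visit, lose 0 of the 574 days.

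Step 4, from days to scans. This needs an assumption, because no scan timing is given.

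- Constant dropout hazard with 20% lost by Day 533, scans counted over Days 2-538: 76.6% of ET scans excluded.
- ET scans uniform from Day 240 to Day 538: 168/299 = 56.2%.
- From Day 324: 168/215 = 78.1%.
- From Day 408: 84/131 = 64.1%.
- From Day 450: 42/89 = 47.2%.
- From Day 492: 0%.

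Step 5, test the obvious remedy. The mid-point of the two MRI targets is (281 + 533)/2 = 407, so ECG-type windows would be Days 2-407 and 408-659, with no excluded day. But 6.1.5 also has precedence rules: within a window a scheduled result beats an unscheduled one, and an ET result replaces a scheduled one. An unscheduled Week 16 scan would therefore still lose to the scheduled Week 40 scan, and a Day 365 ET scan would displace a genuine Week 40 scan.

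**The case against.** A reader might infer that 6.1.5 and 9.7 cannot both be followed. The documents do not support that. Week 76/ET/ED is the Appendix A column label, and the SAP repeats it for laboratory tests, vital signs, ECG, examinations and C-SSRS, all of which are windowed too. On that reading 9.7 says when MRI is collected and 6.1.5 says where it is counted. What stands is that, so read, an ET scan collected under 9.7 goes uncounted on most days of follow-up, which 9.7 does not acknowledge.

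A reader might also infer that most ET scans are lost, or that about 30 scans are at risk (20% dropout × 150). Neither is established. The 71% is a share of days, and Step 4 shows that it does not carry over if ET scans cluster late. The figure of 30 treats every dropout as scanned, yet Protocol Section 9 omits MRI from its early-discontinuation procedures; only the combined Week 76/ET visit in Protocol 7.1.7 and Appendix A implies an ET scan. The early stop may have added ET visits, but no count of scans is given, and SAP 6.1.4 regards that stop as unrelated to treatment and outcome.

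The loss is also limited. MRI findings are listed (9.7) and unscheduled visits stay in listings (6.1.5). A clinically significant finding recorded as an adverse event reaches the adverse-event tables, which do not depend on visit windows. Volumetric MRI follows the efficacy part of 6.1.5, which maps to the nearest scheduled visit and does not repeat the exclusion. No hypothesis test is involved, and scans of participants outside the sub-study are not in this table under any windows.

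These points narrow the concern. They do not explain why ECG was given gap-free windows and MRI was not.

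**Conclusion.** The point holds for one descriptive table. Read literally, SAP 6.1.5 leaves out of Table 14.3.11.1 any ET or unscheduled sub-study MRI on 406 of the 574 days that Table 2.1 covers (71%). This rests on MRI safety findings falling under Table 2.1, which the table's title and the placement of 9.7 support. How many scans are affected is unknown. Efficacy conclusions are untouched and the data are not lost, but the summary meant to show new MRI abnormalities would omit off-schedule scans by rule. It is worth correcting because the correction is nearly free.

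**What to change.** In SAP 6.1.5, exempt MRI safety findings from the exclusion of assessments that land in a window where they are not scheduled. In SAP 9.7 and Table 14.3.11.1, add an *any post-baseline MRI* row by treatment group, counting participants with a new clinically significant abnormality and participants with new microhemorrhages. Use all scheduled, ET and unscheduled scans of MRI sub-study participants. Keep the by-visit Week 40 and Week 76 rows on their present windows, so that their time labels keep their meaning. Do not rely on wide ECG-type windows alone, for the reason in Step 5 of the working.

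The cost is one output row on scans already acquired. Its drawback is that it carries no fixed time label. If the data are already unblinded, label the row post hoc, as SAP Section 1 requires for unplanned analyses.

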6.1.6. Pooling of Sites

Sites with < 2 participants in any treatment arm at Week 76 will be pooled into a common site. All sites with ≥ 2 participants in both treatment arms at Week 76 will not be pooled.

6.1.7. Derived Variables and Conventions

Age: the age at baseline will be used.

Alzheimer's disease status

- MMSE = 21-27 (mild dementia)
- MMSE = 16-20 (moderate dementia)

Change from baseline = post-baseline value at timepoint – value at baseline

Time since diagnosis of AD (months) = (date of first dose – date of diagnosis) / 30.4375

Treatment duration (days) = (date of last dose of study drug – date of first dose of study drug) +1

Study Drug Exposure = treatment duration (days), that is the number of days a participant is on study drug will be calculated as the number of days from date of first dose to date of last dose plus 1.

Study Drug Compliance (%) = 100 x Total number of tablets taken / Total number of expected tablets. That is, study medication compliance will be calculated based on the numbers of tablets dispensed minus the number of tablets returned divided by the expected number of tablets based on the duration of the participant's participation in the study.

Study drug compliance will not be calculated for participants whose date of last study drug is unknown.

Total Dose (mg) = \sum [Number of doses taken_i x Dose received (mg)_i] where,

[figure not shown]
i = 1 to k, (k = number of time periods participant is receiving a constant dose)

Average Daily Dose (mg/day) = Total Dose (mg) / Treatment Duration (days)

Dose variables (dose, total dose, and average daily dose) not calculated for placebo participants.

The iADRS for this trial is a composite endpoint that combines scores from the 12-item AD Assessment Scale-Cognitive subscale (ADAS-Cog12) and the AD Cooperative Study - instrumental Activities of Daily Living (ADCS-iADL). The ADCS-iADL is defined as items 6a and 7-23 of the ADCS-ADL.

Version 1.0 | 28-Feb-2025 Page 22 of 56

iADRS score = [-1(ADAS-Cog12) + 80] + ADCS-iADL

6.1.8. Data Adjustments/Handling/Conventions

All collected data will be presented in listings or Clinical Data Interchange Standards Consortium (CDISC) datasets. Analysis results will be presented and summarized in either tables and/or figures. Data not participant to analysis according to this plan will not appear in any tables or graphs but will be included in the data listings.

All p-values will be displayed in four decimals and rounded using standard scientific notation (e.g., 0.XXXX). If a *p-value* less than 0.0001 occurs, it will be shown in tables as < 0.0001.

The version 24.0 of the Medical Dictionary for Regulatory Activities (MedDRA) will be used to classify all AEs by system organ class (SOC) and preferred term (PT).

Prior and concomitant medications will be classified using Anatomical Therapeutic Chemical class (ATC level 2) and preferred term (ATC level 4) from World Health Organization Drug Dictionary (WHO-DD), WHODrug Global B3 version March2021.

Medications that start before the first dose of study drug are considered prior medications whether or not they were stopped prior to the first dose of study drug. Any medication continuing or starting on or after the first dose of study drug will be considered as concomitant. If a medication starts prior to the first dose of study drug and continues after the first dose of study drug, the medication will be considered as both prior and concomitant.

Adverse events or medications with entirely missing start dates will be classified as treatmentemergent or concomitant, as appropriate.

For partial AE or medication start dates: (a) if only the day is missing, and the month and year match the first dose date and the end date is on or after the first dose date, or AE/medication is ongoing, then the date is assigned the first dose date thus the event/medication will be considered as treatment-emergent/concomitant; if the month and/or year do not match the first dose date or the end date is prior to the first dose date, then the day is assigned the first day of the month (01); (b) if month or the day and month are missing, and the year matches the first dose date and the end date is on or after the first dose date, or AE/medication is ongoing, then the date is assigned the first dose date; if the year does not match the first dose date or the end date is prior to the first dose date, then the day/month are assigned the first day of the year (01JAN).

[figure not shown]
For partial end dates: (a) if only the day is missing, then the day is assigned the last day of the month; (b) if both day and month are missing, they are assigned the last day of the year (31DEC).

For analysis purposes, repeat laboratory results will not be used unless the original value is indicated as missing or invalid. In such cases, the first non-missing repeat value will be used for data analysis. The international system of units (SI) will be used in reporting all laboratory values.

Participants will be analyzed by the treatment received for all safety and tolerability assessments.

Participants are stratified through the IRT system based upon MMSE score entered. Once an MMSE score is entered, that participant is randomized to either high MMSE (21-27) or low MMSE (16-20) strata. At study start, it was decided to stratify participants in this manner so there would be a balance in the number of participants on placebo vs active drug (and within treatment arms) within each stratum. The stratification of the participants does not impact their probability of being

Version 1.0 | 28-Feb-2025 Page 23 of 56

assigned to different treatment arms. Once randomized through IRT, the MMSE score and the stratification assigned cannot be changed.

For instances where the MMSE score was incorrectly entered into IRT, the MMSE score given by the vendor will be used to calculate the strata for safety and efficacy analyses if there are any subgroup analyses.

All collected data will be presented in listings. Data not subject to analysis according to this plan will not appear in any tables or graphs but will be included only in the data listings.

A treatment related AE is any AE with a relationship to the study drug of "Possibly Related" or "Probably Related" or "Reasonable Possibility".

If partial dates occur, the convention for replacing missing dates for the purpose of statistical analysis is as follows: if just day is missing then the day assigned is the first day of the month or the date of first dose (if in the same month), whichever is later; if just month is missing then the month assigned is the month of the first dose, unless that results in a date before the first dose in which case the month after the first dose is used; and if both month and day are missing then the month assigned is the month of the first dose and the day assigned is either the first day of the month or the first dose date, whichever is later.

If partial times occur, the convention is as follows: if the missing time occurs on the day of the first dose and both the hour and minute are missing then the time assigned is the time of the first dose, otherwise if both the hour and minute are missing and the date is not the date of first dose the time assigned is 12:00; if the date is the same as the date of the first dose and only hour is missing the hour assigned is 12 or the hour of first dose, whichever is later, and if the date is the same as the date of first dose and only the minute is missing the minute assigned is 30 or the minute of first dose, whichever is later. Otherwise, the hour assigned is 12 if the hour is missing and the date is not the same as the date of first dose and the minute assigned is 30 is the date is not the same as the date of first dose.

These conventions will be applied only to adverse event onset dates and times with the following precaution: if the missing date and time reflect the date and time of onset of an adverse event, the modified date and time will be constructed to match the first documented date/time post drug administration while preserving the order in which the AE was reported in the CRF.

[figure not shown]
7. Study Participants and Demographics

Participant disposition, demographics and other baseline characteristics, prior medications, and study drug exposure and compliance will be summarized by randomized treatment group and overall, using the ITT analysis set, unless otherwise specified below in each section.

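### SAP 6.1.8 gives two rules for partial AE onset dates and no precedence; the rule without an end-date check can make an AE that ended before dosing treatment-emergent

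*SAP*

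**What the plan says.** SAP 6.1.8 deals with partial AE onset dates twice.

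**First rule.** It opens "For partial AE or medication start dates: (a) if only the day is missing" and assigns the first-dose date only when the known parts of the start date match first dose and the event either ended on or after first dose or is ongoing. Otherwise, that is, "if the month and/or year do not match the first dose date or the end date is prior to the first dose date", the day becomes 01. When the month, or the day and month, are missing, the same logic works on the year, and the fallback is 1 January.

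**Second rule.** Later in the section, the rule begins "if just day is missing then the day assigned is the first day of the month or the date of first dose"; with its limit, the choice is "the first day of the month or the date of first dose (if in the same month), whichever is later". With only the month missing, it takes the first-dose month, "unless that results in a date before the first dose in which case the month after the first dose is used". With both missing, it takes the first-dose month and the later of day 1 and the first-dose date. No branch looks at the end date.

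**Scope.** After the partial-time conventions, the section says: "These conventions will be applied only to adverse event onset dates and times". A precaution follows that steers the imputed onset to the first documented time after dosing; it does not mention the end date either.

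SAP 6.1.4 refers to 6.1.8 for incomplete AE dates without choosing between the rules. SAP 9.1 classes an AE as treatment-emergent if it first occurred on or after the first-dose date, and bases AE summaries on TEAEs unless stated otherwise.

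**The concern.** Both rules govern the same variable. The scope sentence rules out the natural reconciliation, that the second rule is meant for medications or other dates. A programmer must therefore choose, and the choice can decide whether an event enters the TEAE tables.

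The second rule can also produce a record that cannot be true: an onset later than a known end date. Treating an event as treatment-emergent when its timing is in doubt is a normal conservative convention. Here there is no doubt, because the end date shows that the event was over before the first dose.

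Such events can exist. Protocol version 3.0, section 10.1, starts AE monitoring after informed consent, and section 7.1.1 allows a screening period of up to 60 days.

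**Working it through.** There is no plan figure to reproduce. The check applies each rule as written and compares the imputed onset with first dose (SAP 9.1: a TEAE if onset is on or after first dose) and with the end date.

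**Main example.** Start ??-Mar-2023, end 10-Mar-2023, first dose 20-Mar-2023.
- First rule: the month and year match, but the end (10-Mar) is before first dose (20-Mar), so the onset is 01-Mar. Since 01-Mar < 20-Mar, it is not a TEAE.
- Second rule: the later of 01-Mar and 20-Mar is 20-Mar. Since 20-Mar ≥ 20-Mar, it is a TEAE, and its onset is 20 − 10 = 10 days after its end.

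**Other patterns.** First dose 15-Jun-2023, end 10-Jun-2023.

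| Recorded start | First rule | Second rule |
|---|---|---|
| ??-Jun-2023 | 01-Jun, not a TEAE | 15-Jun, TEAE, 5 days after end |
| ??-???-2023 | 01-Jan, not a TEAE | 15-Jun, TEAE, 5 days after end |
| 05-???-2023 | 01-Jan, not a TEAE | 05-Jun is before first dose, so 05-Jul: TEAE, 25 days after end |
| ??-May-2023 | 01-May, not a TEAE | 01-May, not a TEAE |

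The last row marks the limit: with only the day missing and an earlier known month, the rules agree. They also agree, on the first-dose date, when only the day is missing, the month is the first-dose month and the event is ongoing or ended on or after first dose.

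**Check that the two situations are complete.** Both rules were run for every first-dose day in 2023 and every onset/end pair lying wholly in the preceding 60 days, with a complete end date. That is 60 × 61 / 2 = 1,830 pairs per day, and 365 × 1,830 = 667,950 combinations. Where the second rule is silent on the year, the recorded year was kept.

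| Missing part | First rule: TEAEs | Second rule: TEAEs |
|---|---|---|
| Day | 0 | 56,354: all cases with onset in the first-dose month, no others |
| Month, or day and month | 0 | 594,140: all cases with onset in the first-dose year, no others |

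Every TEAE created by the second rule had its onset after its end date. These counts describe a grid of dates and test the logic. They do not estimate how many trial events are affected.

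**The case against.** The strongest reply is that little turns on this. An affected event needs a pre-dose AE, a suitable partial onset and a complete end date before first dose. If the end date is also partial and falls in the first-dose month, 6.1.8 imputes it to month end, and the first rule then assigns the first-dose date too.

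The pool of pre-dose AEs is also limited. Under protocol version 2.0, section 10.1, AE monitoring began at dosing, and SAP 9.1.2 shows that AEs from participants consented under that version are in the data. Under version 3.0, unexpected abnormal screening laboratory results go to medical history, and screening-period AEs are recorded as having no reasonable possibility of drug causation, so correctly recorded ones would stay out of the drug-related tables. SAP section 9 makes safety analysis descriptive unless otherwise specified. All of this stands and keeps the point minor; none of it reconciles the two rules.

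A reader might infer more than the documents support:
- **That any AE ending before dosing becomes a TEAE.** The same-month condition in the second rule prevents this when only the day is missing and the known month is earlier.
- **That post-dose differences also change the tables.** For a start of ??-???-2024 with first dose 15-Jun-2023, the rules give 01-Jan-2024 and, if the recorded year is kept, 01-Jun-2024. Both are TEAEs, and no planned AE table uses time to onset, so the difference would show only in onset dates.
- **That the error favours one arm.** Neither rule refers to treatment.

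The first rule has rough edges of its own: its wording on ongoing events can be misread, and with only the month missing it overwrites a known day. Neither gives an onset after a known end date. Stating precedence would resolve the conflict as well as deletion would.

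**Conclusion.** The point holds within its limits. SAP 6.1.8 contains two rules for the same variable without precedence, and one of them turns an AE with a known end date before first dose into a TEAE with an impossible onset. That happens when only the day is missing and the onset month is the first-dose month, or when the month (with or without the day) is missing and the onset year is the first-dose year. The second situation assumes that the recorded year is kept, which the rule does not say.

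The effect is on TEAE incidence tables, and the misclassification can only add TEAEs. Its size cannot be computed, because the documents do not say how many AEs have partial onset dates; it is likely small. Affected events would come mainly from participants under protocol version 3.0. This is an inexpensive correction to a wrong rule and does not threaten the trial's safety conclusions.

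**What to change.** In SAP 6.1.8, delete the later partial-date convention and the AE-onset precaution that follows the partial-time conventions, or state that the earlier, end-date-aware rule takes precedence for AE onset dates. The earlier rule already covers a missing day, a missing month and both, so deletion leaves no gap. Keep the partial-time conventions, which do not conflict with anything, and reword the scope sentence to refer to times only.

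Add one line that can be checked in the data: an AE with a known end date before first dose is never given an onset after that end date.

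The cost is a text edit and, if the onset imputation has already been programmed from the second rule, a rerun of the TEAE flag. No data collection changes.
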